
Phase 1 - Recruitment, Randomization, Training, Student Screening, and Baseline

Evaluations: In Phase 1, teachers will be randomly selected from the pool of interested participants and randomized to TAPES or TAT. Once randomized, teachers will complete their assigned training. Teachers will then identify potentially eligible students from their classes and provide information about the study to their parents. Interested parents will contact study staff and complete a brief phone screen. Students who appear eligible based on the phone screen (e.g.,

have elevated anxiety; are in elementary school) will be invited to complete informed consent and a full baseline evaluation with an IE (see Table 1 for measures). Families who "pass" the baseline evaluation (i.e., student obtains a *t* score of 60 on Spence Children's Anxiety Scale (SCAS) and/or a CSR of at least 3 on the ADIS-V) will be considered eligible (see Inclusion/Exclusion criteria below).

Phase 2 – TAPES/TAT Implementation: Teachers will implement TAPES or TAT depending on their random assignment over 8 weeks from child enrollment.

Phase 3 - Post- and Follow-up Evaluations: At the end of the 8 weeks, teachers and children in both groups will complete a post evaluation (see Table of Measures). Teachers, students, and parents will complete a TAPES satisfaction measure and provide feedback to enhance the protocol. Teachers will complete an exit interview. Students who need mental health services will be referred to the school counselor or community provider for treatment. A 3 month follow-up evaluation to assess sustained use of TAPES/TAT skills will be conducted.

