Child Participants. A total of 80 students will participate (20 in the open trials and 60 in the RCT). Within the participating CT districts there are 26 elementary schools and 6,000 students. The student body within CT is diverse in terms of gender, socioeconomic status, and racial/ethnic background (12.3% African American, 22.1% Hispanic/Latino, 57.3% Caucasian, 4.8% Asian, 2.5% two or more Races; 32.9% receive free/reduced priced meals). Children of all races/ethnicities may be eligible to participate and will depend on who volunteers. Child Inclusion/Exclusion Criteria. Inclusion/exclusion criteria for open trials and the pilot RCT were crafted to maximize the generalizability of findings. Because the *primary* aim of this study

were crafted to maximize the generalizability of findings. Because the *primary* aim of this study is to evaluate changes in teacher behavior, and because children whose teacher is randomly assigned to TAT may not receive any evidenced-based assistance, children identified as needing treatment based on the diagnostic interview (regardless of group) will be referred for services. Students receiving services will also be enrolled; all service use will be documented over the course of the study. This approach mimics what naturally occurs in the classroom—that is teachers frequently work with students who may be in outpatient or school-based treatment. Inclusion Criteria: All children must: 1) attend a CT elementary school (i.e., ages 5-12 inclusively); and 2) have elevated anxiety symptoms (i.e., a total SCAS *t* score \geq 60 based on parent and/or child report and/or a clinician severity rating [CSR] of 3 or greater on the ADIS) Students will be excluded if they: 1) have a medical or psychiatric condition contraindicating the study participation (based on clinical interview such as recent suicidality). Ambiguous cases will be decided by the PIs and the school teacher.

Child Recruitment. Teachers will identify potentially eligible youth from their classroom, describe the study to their parents and provide them with study contact information. Parents will

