- Anxiety Disorders Interview Schedule for DSM-V, Parent and Child Versions (ADIS-V-C; Silverman & Albano, in press) is considered the gold standard for assessing anxiety diagnoses and severity. Impairment ratings are generated for each disorder using the Clinician Severity Rating (CSR, range = 0.8; ≥ 4 required to assign a diagnosis). The ADIS-C has good test-retest reliability for the parent interview (r = 0.98) and for the child interview (r = 0.93; Silverman et al., 1999a, 1999b, 2001) and is sensitive to intervention effects ([name] et al., 2012). - Clinical Global Impression – Severity (CGI-S) and Improvement (CGI-I) Scales (Guy, 1976) is a measure of global anxiety severity ranging from 1 (normal, not at all ill) to 7 (extremely ill) at all time points. The CGI-I is assigned at post and follow-up assessments to provide a global rating of clinical improvement in anxiety symptoms since the baseline assessment. Scores on the CGI-I range from 1 (very much improved) to 7 (very much worse). Both measures are widely used in child treatment trials to assess symptom severity and improvement (Walkup et al., 2008). - The Children's Global Assessment Scale (CGAS; Shaffer et al., 1983) is used to describe a child's global impairment and functioning at home, school, and with peers on a scale of 1 (gross impairment) to 100 (superior functioning). The CGAS has been used in child anxiety treatment studies to monitor changes in global functioning (e.g., RUPP Study Group, 2002). - Columbia Suicide Severity Rating Scale, Child and Parent Versions (C-SSRS; Posner et al., 2008) is a 6-item measure used to screen for recent suicidal ideation. The C-SSRS demonstrates strong internal consistency and sensitivity to change over time (Posner et al., 2011).

- Spence Children's Anxiety Scale, Child and Parent Versions (SCAS; Spence, 1997, 1998) is a 38-item measure rated for frequency of occurrence (0 never to 3 always) of a broad range of anxiety symptoms. The SCAS–C and SCAS–P have sound psychometric properties, with

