School	Asses the child feeling towards	Child	BL, PO,	1 min
Connectedness	school/teacher		FU	
School Refusal	Assess school absences, early	IE	BL, PO,	1 min
Questionnaire	dismissals, and school nurse or		FU	
	counselor visits attributed to anxiety			
Mental Health			1	
Anxiety	Assess child anxiety symptoms and	IE	BL, PO,	60 mins
Disorders	severity		FU	
Interview				
Schedule, Child				
Version (ADIS-				
C	A 11 · 1	TD	DI DO	1 .
Clinical Global	Assess overall severity and	IE	BL, PO,	1 min
Impression –	improvement of anxiety symptoms		FU	
Severity (CGI-				
S) and				
Improvement				
(CGI-I) Scales	A 1.1.12 11.C	IF		1 .
The Children's	Assess child s overall functioning	IE	BL, PO,	1 min
Global	across disorders		FU	
Assessment $S_{acle}(CCAS)$				
Columbia	Saraan far shild guisidality	IE	DI	1 min
Columbia Suicido Scucuitu	Screen for child suicidality	IE	BL	1 min
Bating Souls				
(CSSPS)				
(CSSKS)	A goog shild anyiety symptoms	Doront/		5 min
Spence Children's	Assess child anxiety symptoms	Child	BL, PO,	5 11111
Anvioto Scalo		Ciniu	ru	
Family Scale	Assess parent and teacher	Darent/	BI DO	5 min
Accommodation	accommodation behaviors in	Teacher	FU	5 11111
	response to child's anyiety	1 cacilei	10	
L	response to ennu s anately	l	 	

· · · · ·	1	T	T	1
Scale – Anxiety				
(FASA)				
Strength and	Assess child	Teacher	BL, PO,	10 min
Difficulties	internalizing/externalizing		FU	
Questionnaire	symptoms			
Teacher	Assess child inattentive behaviors in	Teacher	BL, PO,	1 min
Observation of	the classroom		FU	
Classroom				
Adaptation				
Checklist				
(TOCA-C)				
Avoidance	Assess the top three most significant	Teacher,	BL, PO,	1 min
Hierarchy	anxious/avoidant behaviors	Parent,	FU	
	exhibited in school and at home	IE		
Additional Study	y Measures			
Demographics	Assesses child/family information	Parent	BL	10 min
Form				
Service	Assess changes in	IE	BL, PO,	5 min
Utilization	psychological/psychiatric services in		FU	
Form	school and community			
PHQ	Assess parent and teacher anxiety	Parent,	BL, PO,	1 min
	and mood symptoms	Teacher	FU	
~				
Sub study Measu	ures	1_		l
School	Assess the study child's attendance,	Parent	BL, PO,	5 min
Attendance,	disciplinary actions, and number of		FU	
Discipline, and	parents missed work days			
Work				
Child Health	Assess student's overall health and	Parent	RL PO	2 min
Utility 9D	functioning	Child	FU	2 11111
(CHU9D)	Tunctioning	Ciniu	10	
Total time for each assessment: Teacher 30 min: Parent 50 min: Child: 50 min				

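### The C-SSRS is scheduled at baseline only; repeating it at the post and 3-month evaluations would be a low-cost child-safety improvement (about 2 to 4 evaluator hours in the RCT), not the correction of an error

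*Combined protocol and SAP*

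**What the plan says.** **The instrument.** Under Student Mental Health Outcomes, the C-SSRS (child and parent versions) "is a 6-item measure used to screen for recent suicidal ideation". The same entry credits it with being sensitive to change. In Table 1 its purpose is "Screen for child suicidality", the rater is the IE, the time point is BL and the completion time is 1 minute.

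**Its role at entry.** Child Inclusion/Exclusion Criteria exclude a child with a condition that contraindicates participation, "based on clinical interview such as recent suicidality".

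**Referral.** The same section concedes that "children whose teacher is randomly assigned to TAT may not receive any evidenced-based assistance", and for that reason "children identified as needing treatment based on the diagnostic interview (regardless of group) will be referred for services". The Phase 3 description adds: "Students who need mental health services will be referred to the school counselor or community provider for treatment".

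**What is repeated.** The ADIS, CGI, CGAS, SCAS, FASA, SDQ, TOCA-C and Avoidance Hierarchy are all listed at BL, PO and FU. The ADIS "is considered the gold standard for assessing anxiety diagnoses and severity". Of the improvement scale the plan says: "The CGI-I is assigned at post and follow-up assessments to provide a global rating of clinical improvement in anxiety symptoms since the baseline assessment". The CGAS is described as a rating of global functioning.

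**The concern.** The one instrument described as detecting suicidal ideation is used once, while the other eight rows of the Mental Health block in Table 1 are used three times. The plan regards recent suicidality as serious enough to keep a child out of the study. A child could develop it after entry, and the available text schedules no direct question that would bring it out.

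Referral is the plan's answer to the possibility that control-arm children go without effective help. At the later visits that referral depends on what the evaluator learns there. As described, the repeated measures ask about anxiety, functioning, accommodation, avoidance, classroom behaviour and concentration. A concern about suicidality would have to surface indirectly, or through interview content that the documents do not spell out. What is at stake is the safety of children aged 5 to 12 with elevated anxiety, not the validity of any comparison.

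**Working it through.** The plan has no calculated figure to reproduce here. The check is a count of scheduled time points followed by burden arithmetic.

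**1. Schedule.** The RCT has three child evaluations: baseline, post (after 8 weeks) and 3-month follow-up. The C-SSRS is at 1 of the 3. In the Mental Health block of Table 1 there are 9 rows: 8 at BL, PO and FU, and 1 (the C-SSRS) at BL.

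**2. Time after the only screen.** The available text does not say whether the 3 months run from the post evaluation or from baseline.
- From post: 8 + about 13 = about 21 weeks.
- From baseline: about 13 weeks.

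The point is the same under either reading.

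**3. Added evaluator time in the RCT.** Inputs: a maximum of 60 children (Stage 3), 2 later evaluations, and 1 minute per administration (Table 1). Two minutes is an assumption for the case where the child and parent versions take 1 minute each.
- 60 × 2 × 1 = 120 minutes = 2 hours.
- 60 × 2 × 2 = 240 minutes = 4 hours.

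**4. If open-trial children are included.** There are 20 of them. As an upper bound, giving them two later evaluations as well makes (60 + 20) × 2 × 1 = 160 minutes (2.7 hours) to (60 + 20) × 2 × 2 = 320 minutes (5.3 hours).

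**5. Share of a visit.** IE-rated child measures listed at PO and FU in Table 1: ADIS 60 + CGI 1 + CGAS 1 + Numbers Reversed 5 + Woodcock-Johnson Achievement 20 + School Refusal 1 + Service Utilization 5 + Avoidance Hierarchy 1 = 94 minutes.
- 1/94 = 1.1%; 2/94 = 2.1%.
- Against the 50-minute child total at the foot of Table 1: 1/50 = 2%; 2/50 = 4%.

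**6. Possible yield (illustration only).** The documents give no rate of new ideation. Assume a proportion p of 60 children, independently, have new ideation by PO or FU. Expected cases are 60p, and the chance of at least one is 1 − (1 − p)^60.

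| Assumed p | Expected cases | Chance of at least one |
|---|---|---|
| 0.5% | 0.3 | 0.26 |
| 1% | 0.6 | 0.45 |
| 3% | 1.8 | 0.84 |
| 5% | 3.0 | 0.95 |

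The range is wide and rests wholly on the assumed rates.

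**7. Effect on the statistics.** The primary outcomes are teacher knowledge and observed teacher skills. The power statement uses teacher knowledge and the SCAS. The C-SSRS enters neither.

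**The case against.** The strongest reply is that nothing is wrong. The text calls the C-SSRS a screen, Table 1 gives it a screening purpose, and suicidality is an entry criterion, so purpose and schedule agree. Comparing it with repeated outcome measures is not like with like. This stands: the point is a suggested improvement, and a reader who inferred a scheduling error or an internal contradiction would be going beyond the documents.

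A second reply is that the later visits are not clinically empty. Evaluators with child mental health degrees repeat a 60-minute interview, and the exclusion wording itself treats a clinical interview as a way to identify suicidality. The CHU9D and the Service Utilization Form are repeated, teachers complete a weekly attendance and services form, and weekly consultation with the PIs is offered for each active TAPES student. This stands in part. Any of these might bring risk to light, and the documents do not settle whether the ADIS, CGI or CGAS asks about suicidality. None, however, is described as a suicidality screen, and the weekly consultation covers the TAPES arm only.

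A third reply is that a response procedure may exist in pages not available for review, including the consent pages. This stands fully. One might infer from the available text that the study has no plan for a positive screen, or no same-day response. The documents do not support that inference.

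Finally, calling the change cheap counts administration time only. That is correct, and the time needed to deal with positives remains unestimated.

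**Conclusion.** The point holds as an inexpensive safety improvement. The C-SSRS is scheduled at 1 of 3 RCT evaluations, and no available text describes a suicidality screen at the other two, where a qualified evaluator is already interviewing the child. Adding it would take 2 to 4 evaluator hours over the RCT and gives the existing referral step a direct source of information.

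This rests on the Table 1 completion time of 1 minute, on the maximum of 60 children all attending both later evaluations, and on the repeated interviews not already containing an equivalent question. If they do contain one, it is enough for the plan to say so.

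The conclusion does not extend to the study's overall handling of suicide risk, about which no claim is made. Nor does the interval of 13 to 21 weeks mean that children go unobserved for that long. The primary outcomes, the analysis and the power are untouched.

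**What to change.** In Table 1, change the C-SSRS time point from BL to BL, PO, FU, and state that at PO and FU it is asked about the period since the last evaluation. If open-trial children are to be covered, apply the same rule at each of their later evaluations.

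Add one sentence saying that a positive screen at any visit is handled under the risk procedure that applies to a positive baseline screen, with a cross-reference to it. If no such procedure is written down, one is needed. The Phase 3 referral to a school counselor or community provider is a routine route and does not by itself serve as an acute-risk pathway.

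The cost is one table cell, one sentence and the evaluator time worked out above, with no new instrument, visit or staff. Clinician time for following up positives comes on top, including those that prove not to be acute, and the documents give no basis for estimating it. The Measures section already provides for revising the battery after development-team and open-trial feedback. Whether the change can still precede the RCT is not known, because the available text does not say which stage was under way at the protocol date. If the RCT has begun, the change can apply to the evaluations that remain.

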-Teacher Knowledge Assessment is a 26-item short answer and multiple choice test of anxiety reduction strategies to gauge teachers' prior knowledge and the effectiveness of training. This measure was adapted from an existing knowledge assessment test for school clinicians, which showed an increase in knowledge pre to post-training ([name] et al., 2008).

-*Classroom Observation of Teachers Skills* is a form completed during direct observations of the teacher during normal class activities (e.g., math or reading). The observations are coded by tallying the frequency of specific behaviors that have a positive or negative impact on student anxiety. Using a 5 point Likert scale, observers provide an overall rating of teacher's behavior in both domains.

Usability Measures- The following measures assess whether teachers can understand and learn how to use the skills and whether they can implement the skills effectively and efficiently.

- Teacher Knowledge Assessment (above) will assess ability to learn skills.

- *Classroom Observation of Teachers Skills* (above) will assess use of skills in the classroom. -*Teacher and Child Recruitment Tracker* will be used to record recruitment of teachers/children as well as obstacles to recruitment. Obstacles will be addressed in team meetings and with DT. -*Teacher Time Log* is a form completed by teachers to log the amount of time spent using TAPES/TAT skills with each study student.

Feasibility Measures – The following measures assess whether the training skills can be implemented within an authentic school setting.

-Training Satisfaction and Feedback Questionnaire ([name] et al., 2008, 2011) is a 16-item measure completed anonymously by teachers who rate the helpfulness of training content and format (e.g., role play, videos), overall satisfaction and perceived helpfulness of TAPES/TAT skills for students with anxiety, and their preparedness to conduct conjoint meetings using a 4-point Likert-type scale (1 = not at all helpful to 4 = very helpful). Open-ended questions ask about the most/least helpful aspects of training and suggestions for improvement.

- *TAPES & TAT Satisfaction and Feedback Questionnaires* ([name] et al., 2012) will be adapted for this study from an existing questionnaire and will assess satisfaction and helpfulness of skills used with anxious and in the classroom.

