-Exit Interviews will be conducted with teachers after completing the TAPES program with a student. The PIs will arrange a time to talk with teachers (20 minutes) to obtain qualitative information about perceived barriers to using TAPES, experience implementing TAPES, perceived impact on students, etc. and or suggestions for future implementation. These interviews will take place during the open trials and inform revisions for the RCT.

- *Teacher and Child Retention Tracker* will be used to record the rates/reasons for attrition for both teachers and students and will be discussed weekly in team meetings and with the DT. -*Satisfaction Forms, Meetings 1-5* will be administered to teachers, parents, and students to assess satisfaction with each school-home meeting.

Fidelity of Implementation Measures – The following measures, described above, will assess adherence and quality of implementation of TAPES:

- S-H Fidelity and Quality Measure (Meetings 1-5) is a form assessing the fidelity and quality of TAPES skills based on audio-recorded school-home meetings. The goals of each meeting are

rated for adherence (Was goal accomplished? Yes/No) as well as quality of implementation (1 = Poor to 4 = Very Good), which reflects the accuracy of the presentation, use of elaboration and student-specific examples, and assessment of parent/student understanding.

- *Teacher S-H Meeting Summary Form* is a 16-item measure completed following conjoint meetings. This checklist contains items that measures parent and student involvement, assesses barriers to use, and whether goals were accomplished.

- *Classroom Observations of Teachers Skills* (see above) will be used to assess fidelity. Teacher and Child Measures Linked with TAPES Theory of Change. Several measures will be collected to assess factors that may influence fidelity of TAPES skills and/or are directly linked to the proposed theory of change:

- *Student-Teacher Relationship Scale* (STRS; Pianta, 1992) is a 15-item scale with good psychometric properties that will assess the quality of the teacher-child relationship.

- *Parent-Teacher Relationship Scale* (Vickers & Minke, 1995) is a 24-item measure of teacherparent relationship quality. The measure has good psychometric properties (Dawson & Wymbs, 2016).

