Aim #1: To develop and assess the usability, acceptability and feasibility of TAPES, a teacher training to reduce student anxiety. To address this aim, quantitative and qualitative data collected from the DT's initial review of materials and participants' (teachers, children and parents) data in the open trials will be recorded and synthesized in a descriptive manner. The PIs and DT will use this information to refine TAPES' training materials. Additional information regarding feasibility and acceptability will be collected throughout the study (e.g., obtaining reasons for declining initial participation and reasons for drop outs, and evaluating satisfaction). We will review mean scores on measures of satisfaction (e.g., Training Satisfaction and Feedback Questionnaire, TAPES Satisfaction and Feedback Questionnaire) as well as participants' responses to open ended questions on these measures. Moreover comments from the teacher Exit Interviews will enable us to modify individual components in TAPES to enhance its usability, acceptability and feasibility for Stage three. During the pilot RCT in Stage three, ANCOVA will be used to compare TAPES with TAT in terms of usability, acceptability, and feasibility based on the same satisfaction measures. If needed, we will use teacher-specific (e.g., years of teaching experience, teaching efficacy) and child-specific (e.g., age, baseline anxiety severity) as covariates. For example teachers' rating on intervention acceptability will be modeled as y_{ij} = $\mu + \tau_i + B(x_{ij} - \bar{x}_i) + \varepsilon_{ij}$ where *i* indicates teacher-level randomized intervention-training group assignment, say 1 for TAPES, and 0 for TAT, y_{ij} denotes the rating from the jth teacher in group *i* at post training, x_{ij} denotes teacher-specific covariates, and ε_{ij} denotes the unobserved error term. If the null hypothesis $\tau_0 = \tau_1$ is rejected, it implies that teacher's view on

acceptability depends on their assigned group. In addition, weekly data from *Teacher and Child Recruitment Tracker*, *Teacher Time Log*, and *Teacher and Child Retention Tracker* will be used to assess feasibility.

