burnout, teacher efficacy; teacher behavior) and child characteristics (e.g., gender, age, baseline anxiety symptoms, classroom functioning). To test the main hypothesis, that teachers in TAPES, compared to TAT, will have higher knowledge about anxiety reduction, we will examine scores on the *Teacher Knowledge Assessment* at post-training, and at the end of school year as outcomes in GLM controlling for teacher pre-training score. Let y_i denote the post-training or end of school year test score of teacher i, x_{i1} and x_{i2} denote teacher i's group assignment and pre-training test score, respectively, and ε_i denote resident term. Rejecting $\beta_1 \leq 0$ and $\beta_3 \leq 0$ in the model: $y_i = \beta_0 + \beta_1 \times x_{i1} + \beta_2 \times x_{i2} + \beta_3 \times x_{i1} \times x_{i2} + \varepsilon_i$ suggests that TAPES teachers' post-training test scores are higher and they have a greater gain in knowledge than TAT teachers. Teacher-specific covariates can be added to the above model as needed. To test the hypothesis that TAPES, compared to TAT, will result in greater use of anxiety reduction skills in the classroom, IE's Classroom Observation of Teachers Skills rating for each pair of teacher and anxious student at baseline, post-intervention, and 3-month follow-up will be modeled in GLMM. Now rating, y_{ijk} are nested within teacher k and student j, who is nested within teacher k, in the multilevel equations: Level 1: $y_{ijk} = \pi_{0jk} + \pi_{1jk} \times \text{timepoint}_{ijk} + e_{ijk}$; Level 2: $\pi_{0jk} = \beta_{00k} + r_{0jk}$ and $\pi_{1jk} = \beta_{10k} + r_{1jk}$; Level 3: $\beta_{00k} = \gamma_{000} + \gamma_{001} \times w_k + u_{00k}$ and $\beta_{10k} = \gamma_{100} + \gamma_{101} \times w_k + u_{10k}$; where w_k denotes teacher k's intervention-training group assignment with e, r, and u representing error terms in the respective levels. Teacher-specific (e.g., years of teaching experience, teaching efficacy) and child-specific (e.g., age, baseline anxiety severity) covariates can be added to Levels 2 and 3 equations as needed. Aim #4 (Secondary Outcomes): To examine the impact of TAPES relative to TAT on student outcomes. Change scores on student mental health (e.g., Spence Children's Anxiety Scale, SCAS) and academic achievement (e.g., Woodcock-Johnson Tests of Achievement) from pre-to postintervention and 3-month follow-up will be modeled as GLMM similar to above in Aim 3. **Exploratory aims**: To examine mediators (proposed in the theory of change, see Figure 1 in Appendix) and predictors and moderators (e.g. Teacher Background Form, MBI-Educators Scale) of TAPES impact on teacher knowledge and behavior. Structural equation modeling (SEM) will be used to explore potential predictors (e.g., baseline teacher burnout as measured by MBI-ES), mediators (e.g., subscale scores from the OSTES) and moderators (e.g., years of teacher experience) on teacher behavior change (e.g., change score on the Classroom Observation of Teachers Skills at pre-, post-intervention and 3-month follow-up). Sub study: Aim #1: Assess the direct and indirect cost of pediatric anxiety among youth enrolled in the TAPES intervention. This aim involves the modification of existing measures of direct and indirect cost. These measures will be administered to parents and teachers at existing TAPES assessment time points (i.e. baseline, post intervention and three-month follow up). Aim #1a: Estimating the cost of pediatric anxiety through direct and indirect costs. Aim #2: To examine the child and parent benefit of TAPES compared to UC. This aim involves estimating the cost of TAPES relative to the UC condition in relation to direct and indirect costs. Exploratory Aim: To examine family demographic factors as moderators of pediatric anxiety cost. **Power Analysis.** Although this is a development study proposing a small pilot RCT, attempts were made to estimate statistical power for the key outcomes based on existing literatures on similar measures (see White et al., 2011 for Teacher Knowledge Assessment and Barrett et al., 2005 for child anxiety using the SCAS). Using Optimal Design version 3.0 calculations for both variables were based on an anticipated enrollment of 20 teachers in each group (and 1-2 students per teacher). We assumed a conservative within-teacher ICC of 0.10 (Eldridge et al., 2004) and

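### Aim 1 names single-level ANCOVA for parent and student satisfaction ratings that are nested in randomised teachers; their standard errors come out slightly too small

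*Combined protocol and SAP*

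**What the plan says.** In the Data Analytic Plan, Aim #1 states that in Stage three "ANCOVA will be used to compare TAPES with TAT in terms of usability, acceptability, and feasibility based on the same satisfaction measures". The satisfaction measures it names just before are the Training Satisfaction and Feedback Questionnaire and the TAPES Satisfaction and Feedback Questionnaire. The paragraph allows teacher-specific and "child-specific (e.g., age, baseline anxiety severity) as covariates". It then gives one worked example, whose outcome "denotes the rating from the jth teacher in group" i after training, with teacher covariates and a single error term.

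On who supplies the ratings, Phase 3 of the RCT says: "Teachers, students, and parents will complete a TAPES satisfaction measure and provide feedback to enhance the protocol". Table 1 lists teacher, parent and child as raters of the TAPES questionnaire at the post assessment. The Feasibility Measures section refers to questionnaires for both TAPES and TAT, without listing informants.

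On structure, the Randomization section allocates teachers 1:1, 20 per arm. Stage 3 plans 40 teachers and at most 60 students. The Power Analysis works with 20 teachers per group "and 1-2 students per teacher). We assumed a conservative within-teacher ICC of 0.10". The skills outcome in Aim 3 is modelled with students nested in teachers, and Aim 4 follows the same model.

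**The concern.** Two families who share a teacher rate a programme that the same teacher delivered, so their ratings may be correlated. The teacher was randomised, so the comparison of arms rests on variation between teachers. A single-level model with one row per family takes each row as independent and, with a positive ICC, understates the standard error of the TAPES-TAT contrast.

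ANCOVA cannot easily be read here as shorthand for a mixed model, because the preliminary-analyses paragraph lists ANCOVA, GLM and GLMM as separate methods. The child-level covariates also point to child-linked rows: a teacher with two students has two ages and two baseline severities, and no rule is given for combining them. The stated fallback to non-parametric methods does not deal with clustering.

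At stake is the reliability of the parent- and student-rated acceptability comparisons, which feed the judgement that the training is ready for a larger trial. No primary or secondary outcome is affected.

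**Working it through.** The plan gives no power or precision figure for the satisfaction comparison, so there is none to reproduce.

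**Inputs from the documents**
- 20 teachers per arm (Randomization).
- At most 60 students, so 30 per arm and 1.5 per teacher on average (Stage 3).
- 1-2 students per teacher and a within-teacher ICC of 0.10 (Power Analysis). That ICC was set for the knowledge and child-anxiety calculations; none is given for satisfaction.
- Alpha 0.05 (Power Analysis). Sidedness is not stated; two-sided is assumed.

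**Inputs assumed**
- In each arm, 10 teachers have one student and 10 have two.
- Each informant is analysed separately, and parents and students in both arms give a rating.
- ICCs of 0.30 and 0.50 are used to show a range.

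**Step 1: effective cluster size.** m_w = Σm² / Σm = (10×1 + 10×4) / (10×1 + 10×2) = 50/30 = 1.667.

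**Step 2: design effect.** DE = 1 + (m_w − 1) × ICC = 1 + 0.667 × ICC. The correct standard error is the naive one times √DE.

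**Step 3: true type I error of a nominal 5% test.** 2 × [1 − Φ(1.96/√DE)].

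| ICC | DE | SE multiplier | Type I error | Simulated |
|---|---|---|---|---|
| 0.10 (documents) | 1.067 | 1.033 | 5.8% | 5.7% |
| 0.30 (assumed) | 1.200 | 1.095 | 7.4% | 7.3% |
| 0.50 (assumed) | 1.333 | 1.155 | 9.0% | 8.9% |

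The simulated column is the rejection rate of an ordinary two-sample t-test in 40,000 null trials with this layout.

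**Step 4: sensitivity to the split of students, at ICC 0.10.** With a flat 1.5 per teacher, DE = 1.05 and type I error is 5.6%. If every contributing teacher had two, DE = 1.10, the multiplier is 1.049 and type I error is 6.2%. If every teacher had one, DE = 1 and nothing changes.

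**Step 5: ratings that are not affected.** The training questionnaire "is a 16-item measure completed anonymously by teachers", and Table 1 places it once, after training. With one row per randomised teacher, DE = 1 and single-level ANCOVA is right. The per-meeting forms "will be administered to teachers, parents, and students to" rate each meeting, so they are repeated, but conjoint meetings are described only for TAPES. They have no TAT counterpart to compare.

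**The case against.** The strongest reply is that the model actually written for Aim 1 is correct: it has one rating per teacher, which is the randomised unit. It also fits the plan's wider pattern, since teacher knowledge in Aim 3 has a single-level GLM while student-linked outcomes have a GLMM. On this view the plan is silent on parents and students rather than wrong. The defence of the equation stands in full. The silence does not remove the gap: the equation is offered as an example, ANCOVA is the only method named for the comparison, and the questionnaire has parent and child raters.

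The reply can add that Phase 3 and Table 1 name only a TAPES satisfaction measure, so a between-arm contrast for families is not certain. That is fair. Questionnaires for both conditions are mentioned elsewhere and the stated aim is to compare arms, so the contrast is the likelier reading, but it remains a condition of this point.

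The reply is also right that the effect is small at the ICC the plan calls conservative, that 60 students is a ceiling, and that Aim 1 is largely descriptive.

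A reader might infer more than the documents support:
- **That all Aim 1 error bars are too narrow.** This is not so for any once-per-teacher rating.
- **That one teacher rates the programme twice.** Teachers are paid for measures on each student, but nowhere is the satisfaction form said to be repeated per student.
- **That the inflation is large.** Pooling parent and child rows would give m_w = (20×4 + 20×16)/120 = 3.33 and type I error of 7.8% at ICC 0.10 or 13.3% at 0.30. The plan does not say that informants will be pooled, and every ICC above 0.10 is assumed.

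**Conclusion.** The point holds for parent and student satisfaction ratings, and its severity is minor. If these are compared between arms as Aim 1 states, nesting in the randomised teacher is ignored and the standard error is too small. At the documents' ICC of 0.10 the correct standard error is about 3% larger and type I error is about 5.8% instead of 5%. The error grows only if satisfaction is more strongly shared within a teacher than the plan assumed for its other outcomes, which is plausible but undocumented.

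This rests on 1-2 students per teacher split evenly, separate analysis of each informant, a two-sided 5% test, and family ratings being collected in both arms. Teacher ratings are affected only if the form turns out to be completed once per student.

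**What to change.** Add to Aim #1: parent and student satisfaction ratings will be analysed separately by informant, with a teacher random intercept as in the skills model of Aim 3 and in Aim 4, or as unweighted teacher means; teacher ratings will be treated the same way only if the form is completed once per student; single-level ANCOVA is kept for once-per-teacher ratings. The text should also say whether parents and students in TAT complete the questionnaire, and whether teachers complete it once or per student.

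If teacher means are used, leave them unweighted and average child covariates within teacher. Weighting by the number of ratings assumes that variance falls as 1/m, which is false when the ICC is positive. In simulation, weighted means gave type I error of about 5.1-5.2% at ICC 0.10 and 6.0% at 0.70, while unweighted means held at about 5%.

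No new data are needed. At ICC 0.10 intervals widen by about 3% with the random intercept. Unweighted means cost somewhat more: in units of the rating's total variance, the variance of an arm mean is [10×1 + 10×(0.10 + 0.90/2)]/400 = 0.03875, against 1/30 = 0.03333 for the naive analysis, so the standard error is √1.1625 = 1.08 times the naive one. The random intercept is therefore the more efficient choice. Its variance will be estimated only from teachers with two students, so unweighted means are a sensible fallback if that estimate is unstable.
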